9.2 Data that are reviewed

Describe the data that are reviewed, including safety data, untoward events, and efficacy data.

Achilles tendon healing:

- re-rupture
- deep vein thrombosis
- deep and superficial infection

NMES:

- skin irritation
- excessive pain

Benefits/efficacy:

- self-reported outcomes (questionnaires)
- daily step count
- ability to perform a heel-rise

9.3 Method of collection of safety information

Describe the method by which the safety information will be collected (e.g., with case report forms, at study visits, by telephone calls and with subjects).

Data about tendon healing will be taken during study visits.

9.4 Frequency of data collection

Describe the frequency of data collection, including when safety data collection starts.

Data about tendon healing will be collected at 6, and 12 weeks. Pain, weight bearing, and step count will be recorded daily for the first 6 weeks. Heel-rise evaluation will be performed at week 12.

9.5 Individuals reviewing the data

Identify the individuals who will review the data. The plan might include establishing a data and safety monitoring committee and a plan for reporting data monitoring committee findings to the IRB and the sponsor.

The treating research team will monitor the subject's healing progress. If concerns are found, participants will be asked to see out team physician ([name]) who will determine the proper course of action, i.e., removal from the study, modification of the rehab protocol and/or additional interventions. A NIAMS-appointed Safety Officer (SO) will review the study data on a routine basis.

9.6 Frequency of review of cumulative data

Describe the frequency or periodicity of review of cumulative data.

Cumulative data will be reviewed every two months.

9.7 Statistical tests

Describe the statistical tests for analyzing the safety data to determine whether harms are occurring.

For testing the difference groups and standard treatment, we will quantify the odds ratio and the 95% confidence of AEs or SAEs. If the bottom end of the confidence interval is higher than 1.0, the improvement will be significant.

9.8 Suspension of research

Describe any conditions that trigger an immediate suspension of research.

If the odds ratio of AEs related to the intervention and/or SAEs of the intervention reaches statistical significant levels compared to standard treatment, the study will be suspended immediately.

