7.1 Study Design

Describe and explain the study design.

This is a randomized clinical trial with two groups: control and stimulation. Participants will be randomly assigned to a NMES (active) treatment or control group in a 1:1 ratio. No stratification factors will be considered in the randomization process based on covariates such as gender, activity, and age. In the stimulation group, subjects will receive standard rehabilitation and NMES will be applied to calf muscles 6 weeks after repair surgery. The pad placement and stimulation parameters will be updated in a weekly basis for the stimulation group. The control group will follow standard rehabilitation and will not receive NMES. For both groups, ultrasound evaluation will be performed at week 6 and 12 weeks after surgery. The primary outcome (heel-rise) will be measured at week 12 after repair. Other outcomes (activity level, pain) will be measured daily for the first 6 weeks after repair.

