9.1 Periodic evaluation of data

Describe the plan to periodically evaluate the data collected regarding both harms and benefits to determine whether subjects remain safe.

The research team will monitor the recovery of the participant during standard-of-care visits and determine the occurrence of possible adverse related to Achilles tendon healing (re-rupture, deep vein thrombosis, deep and superficial infection) or the use of NMES (skin irritation and excessive pain).

Research team will capture and report all AEs at every visit. These AEs will be evaluated by a physician study team member ([name]) for their relatedness and severity. If the team member physician ([name]) prescribes a modification in the rehabilitation protocol or additional interventions (surgery), the patient will be removed from the study. Cumulative data will be evaluated every 2 months to determine if incidence of adverse events is higher than the normal (standard of care). The normal (standard of care) incidence of re-ruptures is 5% [4], [25], deep vein thrombosis is 48% [61], infection 2.8% [62], skin irritation 33% [63].

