18.8 Stopping Rules

In studies with a primary safety endpoint or studies with high risk to study subjects, provide the rules that define the circumstances and procedures for interrupting or stopping the study. If an independent Data and Safety Monitoring (DSMB) or Committee (DSMC) is set up for the study, the same stopping rules should be incorporated into the safety analysis plan as well.

The study will be interrupted if AEs (re-rupture, deep venous thrombosis, infections, and skin irritation) occur at a rate higher than that reported for standard of care.

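### The 18.8 stopping rule has no margin for chance (about 90% false interruption at one look at 9.1's own rates), and 9.8 does not set aside disclosed pad-site irritation

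*Combined protocol and SAP*

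**What the plan says.** The plan has two halting rules.

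- **Section 18.8** interrupts the study if "AEs (re-rupture, deep venous thrombosis, infections, and skin irritation) occur at a rate higher than that reported for standard of care". It names no test, margin, minimum number of patients or arm.
- **Section 9.8** suspends the study immediately "If the odds ratio of AEs related to the intervention and/or SAEs of the intervention reaches statistical significant levels compared to standard treatment". Under 9.7, "we will quantify the odds ratio and the 95% confidence of AEs or SAEs", and the criterion is a lower limit above 1.0. The interval method is not named, and neither section says whether events are tested by type or pooled.

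The reported rates are in 9.1: re-rupture 5%, DVT 48%, and "infection 2.8% [62], skin irritation 33% [63"]. All are labelled standard of care, but the title of the reference for the 33% concerns complications of TENS.

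Sections 9.2 and 10.0 list skin irritation as an expected effect of NMES. In 7.1, "The control group will follow standard rehabilitation and will not receive NMES". On timing, 9.6 says "Cumulative data will be reviewed every two months", and 9.5 adds that a Safety Officer "will review the study data on a routine basis".

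**The concern.** A rule that fires on any excess over a benchmark will fire about half the time when the true rate equals the benchmark. With four event types and repeated reviews, an interruption becomes likely even if NMES adds no harm.

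Section 9.8 has a different weakness. Pad-site irritation is a disclosed local effect that patients without pads cannot have as a device-related event. A significant odds ratio for it would tell the investigators what they already expected, yet the text requires immediate suspension.

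At stake is a 50-patient trial being halted for chance variation or for a known minor effect.

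**Working it through.** The plan states no false-halt probability for either rule, so there is no figure to reproduce.

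**Inputs.** 25 patients per arm (8.3); event rates from 9.1. Assumptions: 18.8 is applied to the NMES arm and by event type (9.1 gives no combined rate), all 25 are observed, and there is one look unless stated.

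**Section 18.8.** The rule fires at the smallest count k with k/25 above the reported rate p. Its probability is P(X ≥ k) for X ~ Binomial(25, p).

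| Event | p | 25p | k | P(X ≥ k) |
|---|---|---|---|---|
| Infection | 0.028 | 0.70 | 1 | 0.508 |
| Re-rupture | 0.05 | 1.25 | 2 | 0.358 |
| DVT | 0.48 | 12.0 | 13 | 0.420 |
| Skin irritation | 0.33 | 8.25 | 9 | 0.448 |

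For example, infection is 1 − 0.972^25 = 0.508, and re-rupture is 1 − 0.95^25 − 25 × 0.05 × 0.95^24 = 1 − 0.277 − 0.365 = 0.358.

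- Any of the four, if independent: 1 − 0.492 × 0.642 × 0.580 × 0.552 = 0.899.
- Without irritation: 1 − 0.492 × 0.642 × 0.580 = 0.817.
- Under any dependence, the probability that at least one fires cannot be below the largest single figure, 0.508.

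Repeated looks add to this, because small denominators make one event decisive: a single re-rupture exceeds 5% whenever fewer than 20 patients have been observed (1/19 = 5.3%). For irritation alone at a true 33%, simulated looks at 5, 10, 15, 20 and 25 patients give about 76%. This schedule is assumed, since the accrual period is not stated.

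The irritation figure depends on the true NMES rate. P(X ≥ 9 of 25) is 45% at 33%, 15% at 25% and 5% at 20%.

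**Section 9.8, irritation alone.** I enumerated two independent binomials at 25 per arm. The rule fires when the lower 95% limit exceeds 1, using a logit interval with 0.5 added to every cell, or when two-sided Fisher p < 0.05 with more events on NMES.

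With no control events the firing count can be seen directly:

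- 7 v 0: odds ratio = (7.5 × 25.5)/(18.5 × 0.5) = 20.7; SE of the log = √(1/7.5 + 1/18.5 + 1/0.5 + 1/25.5) = 1.49; lower limit = exp(3.03 − 1.96 × 1.49) = 1.11; Fisher p = 0.010. Both methods fire.
- 6 v 0: lower limit 0.90, Fisher p = 0.022. Only Fisher fires.

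So at 33% v 0% the probabilities are P(X ≥ 7) = 0.768 and P(X ≥ 6) = 0.881. Every pair of rates below is an assumption, except that 33% v 33% follows 9.1's label.

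| NMES v control | Logit | Fisher |
|---|---|---|
| 33% v 0% | 77% | 88% |
| 33% v 10% | 42% | 39% |
| 33% v 33% | 2% | 1% |
| 20% v 0% | 22% | 38% |
| 10% v 0% | 1% | 3% |

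The interval method matters. Adding 0.5 only where a cell is zero gives 47% at 33% v 10%. An uncorrected Wald interval does not exist when controls have no events.

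**Candidate limits.** The smallest count with P(X ≥ k) ≤ 0.025 at 9.1's rates in 25 patients is 4 for infection (0.005), 5 for re-rupture (0.007), 18 for DVT (0.013) and 14 for irritation (0.015). Combined at one look, if independent: 1 − 0.995 × 0.993 × 0.987 × 0.985 = about 0.04.

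**The case against.** Several points on the other side stand.

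- **A reader might infer that 18.8 makes no allowance for irritation.** It does: it names irritation and compares it with 33%. What it lacks is a margin for sampling error.
- **The large 9.8 percentages rest on rates the documents do not state.** No section gives an irritation rate for NMES, and the only figure that could serve for controls is 9.1's 33%. On that label, 9.8 fires in 1-2% of runs, close to its nominal error. A control rate near zero is plausible for a pad-site event, but irritation from another cause, such as the cam boot, is possible. Reading 33% as a stimulation rate rests on a reference title alone.
- **A reader might infer that the two rules contradict each other,** because 7 v 0 trips only 9.8 and 9 v 4 trips only 18.8. They do not: each is a sufficient trigger.
- **Neither section says the trial is terminated.** The words are suspended and interrupted. A physician assesses relatedness and severity, and the Safety Officer reviews the data, so a pause could be resolved.
- **Many early looks inflate the repeated-look figures,** because the first would contain only a few patients.

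The one-look result for 18.8 survives all of this. It uses only 9.1's rates and the planned 25 patients, and needs no control rate. The wording of 9.8 still counts a disclosed, one-arm effect towards suspension; only how often that matters is uncertain.

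**Conclusion.** The main defect is in 18.8 and covers all four event types. With true rates exactly as in 9.1, one look at 25 NMES patients interrupts the study in about 90% of runs if the events are independent, and in at least 51% whatever their dependence. Irritation is not the main driver: the other three events alone give about 82%. If true NMES rates lie below 9.1's, the rule fires less often.

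The defect in 9.8 is real in wording and uncertain in size, from 1-2% to 77-88% at one look over the rates tried. The documents do not support presenting the upper end as the expected behaviour.

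The sponsor should correct both sections. Confidence is high for 18.8 and moderate for 9.8.

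**What to change.** 1. **18.8:** replace the bare comparison with a rule that allows for chance. Either use the between-arm test of 9.7 and 9.8 for re-rupture, DVT and infection, or use exact one-sided 2.5% limits against 9.1's rates (5, 18 and 4 of 25). State the arm and the limits at each interim number.
2. **9.8:** keep the between-arm trigger for SAEs, re-rupture, DVT, infection, and gapping or non-healing (which 10.0 says will be compared). Take expected non-serious pad-site irritation out of it. In 9.7, name the interval method, including for zero cells, and say that events are tested by type.
3. **Irritation and excessive stimulation pain:** monitor both in the NMES arm only, against thresholds agreed with the Safety Officer; for irritation, for example, 14 of 25 against 33%.
4. **9.1:** check the source of the 33% and relabel it if it is a stimulation rate.
5. State the rule's false-halt probability under the actual review schedule, and keep physician and Safety Officer discretion to halt at any time.

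The cost is wording in four sections and one short calculation, with no new data. The downside is less sensitivity to real harm. A limit of 14 of 25 is reached in only 35% of runs at a true irritation rate of 50%. Re-rupture at 20% v 5% is flagged between arms in only 15-20%. The one-arm limit of 5 does better there, P(X ≥ 5) = 58% for Binomial(25, 0.20), but relies on an external rate. This is why item 5 keeps discretion to halt.

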10.0 Risks

List the reasonably foreseeable risks, discomforts, hazards, or inconveniences to the subjects related to the subjects' participation in the research. Include as may be useful for the IRB's consideration, a description of the probability, magnitude, duration and reversibility of the risks. Consider all types of risk including physical, psychological, social, legal, and economic risks. Note: Loss of confidentiality is a potential risk when conducting human subject research.

- If applicable, indicate which procedures may have risks to the subjects that are currently unforeseeable.
- If applicable, indicate which procedures may have risks to an embryo or fetus should the subject be or become pregnant.
- If applicable, describe risks to others who are not subjects.

Risk of Randomization: You will be assigned to a treatment program by chance. The treatment you receive may prove to be less effective or to have more side effects than the other research treatment(s) or other available treatments.

Heel-rise test: The heel-rise testing may cause local tendon pain. The subjects will be informed that if they have a pain level above a 5/10 they should inform the evaluator, stop the test, and avoid strong physical activity for 1 or 2 days.

NMES usage: The device used for this test is FDA approved. There is a minimal risk of infection. Discomfort during and muscle soreness after usage lasting a few days after the test may be experienced. Skin irritation caused by the adhesive pads may also occur. Excessive pain might occur during stimulation, even at the recommended settings. Subjects will be instructed to gradually increase the stimulation intensity up to the recommended level by PT. Subjects will be instructed to contact the research team if the excessive pain occurs at or below the recommended intensity.

Tendon healing: Re-injury of the tendon is also a potential risk. The rate of tendon re-rupture in standard therapy is estimated between 2% and 5% [64]. Gapping or non-healing of the tendon have also been observed in regular therapy. These adverse events may be observed in the participants participating in the study. Statistical analysis will be performed to determine if the risk of these adverse events is higher in the intervention group compared to standard therapy.

Additional Risks

Loss of confidentiality is another risk of participating in this study. To minimize this risk. Identifiable information will be kept locked in the lab. Only the PI and the research personal participating in the study will have access of the key. Identifiable information will be destroyed according to the plan in section 9.0.

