8.2 Sample size determination

If applicable, provide a justification of the sample size outlined in section 8.1 to include reflections on, or calculations of, the power of the study.

Two independent sample proportion comparison test was to compute the sample size using G* Power 3.1. A power analysis was performed based on the proportion of participants able to perform a heel rise at week 12, which is a strong predictor of long-term outcomes. With current rehabilitation strategies, 50% of participants are able to perform a single heel-rise at week 12. A clinically-significant improvement that would justify the application of the proposed treatment would be that 85% of participants would perform a heel-rise. A minimum of 22 subjects should be recruited in each group to achieve 80% power, with 5% significant level, equal allocation, to detect a significant difference between the two groups. Assuming an attrition rate similar to our previous studies of 10%, the total number of subjects in the NMES group should be 25.

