8.3 Statistical methods

Describe the statistical methods (or non-statistical methods of analysis) that will be employed.

We will recruit 25 participants to participate in the NMES intervention and 25 for standard rehabilitation (control). Summary statistics for variables of interest including recruitment, retention, adherence, and reported pain will be calculated. To test the difference between groups (NMES and control), we will quantify the odds ratio and the 95% confidence interval of performing a single heel-rise test. If the bottom end of the confidence interval is higher than 1.0, the improvement will be significant. Chi-square goodness of fit will be used to study the associations between groups and covariates such as gender, activity, and age. Cochran-Mantel-Haenszel test will be used to evaluate the consistency of such associations.

Protocol deviations, such as missing visits, or lost to follow up (within the 10% already considered in the power analysis) will have a negligible effect on the statistical analysis since the proposed analysis can have unbalanced groups. The planned interim safety analyses will quantify the odds ratio between adverse events in the intervention group and standard of care. If the bottom end of the confidence interval is higher than 1.0, the incidence of AEs in the intervention group will be significant higher than that of standard care.

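### The plan's only between-arm test of re-rupture, gapping and non-healing cannot determine whether NMES raises the risk: at 25 per arm it misses a re-rupture rise from 5% to 20% about 80–89% of the time, and the upper confidence limit is given no meaning.

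*Combined protocol and SAP*

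**What the plan says.** Section 10.0 (Risks) names re-rupture, gapping and non-healing, puts re-rupture under standard therapy at 2% to 5%, and then undertakes: "Statistical analysis will be performed to determine if the risk of these adverse events is higher in the intervention group compared to standard therapy".

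The between-arm method is given in three places.

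- Section 8.3, on the interim safety analyses: "If the bottom end of the confidence interval is higher than 1.0, the incidence of AEs in the intervention group will be significant higher" than under standard care.
- Section 9.7 repeats the odds ratio with 95% confidence interval for AEs or SAEs and reads it by the same lower limit.
- Section 9.8 suspends the study on the same criterion: "If the odds ratio of AEs related to the intervention and/or SAEs of the intervention reaches statistical significant levels compared to standard treatment".

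A second rule stands apart. Section 9.1 reviews cumulative incidence every two months against listed reference rates: "The normal (standard of care) incidence of re-ruptures is 5" per cent, with others for DVT, infection and skin irritation. Section 18.8 interrupts the study if these events exceed the rate reported for standard of care, with no significance requirement.

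The trial was sized on heel-rise alone (8.2). No section sets a margin, interprets the upper limit, or states power or precision for any harm.

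**The concern.** NMES deliberately loads a fresh tendon repair, and the protocol itself lists re-injury of the tendon as a potential risk. Section 10.0 says an analysis will settle whether that risk is higher. The only comparison with concurrent controls gives meaning to one outcome, a lower limit above 1.0, and is silent on every other. With few expected events and 25 per arm, the other outcome is likely even if the harm is large. Section 1.1 calls this the second phase of three, so its safety statement will inform the next phase. A bare report of no significant difference could be carried forward as reassurance when the data cannot exclude a several-fold increase.

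**Working it through.** **Inputs.** Arm sizes (8.3): "We will recruit 25 participants to participate in the NMES intervention and 25 for standard rehabilitation (control"). Sizing (8.2): "A minimum of 22 subjects should be recruited in each group to achieve 80% power, with 5% significant level, equal allocation". Heel-rise rates (8.2): "50% of participants are able to perform a single heel-rise at week 12" under current care, against a target that "85% of participants would perform a heel-rise". Background re-rupture is 5% (9.1) or 2–5% (10.0). The plan does not name a method for the odds-ratio interval, so three are shown. The fourfold rise (5% to 20%, 2% to 8%) is assumed for this check.

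**The plan's own figure.** For 50% v 85% with a pooled variance, n = [z_α √(2 × 0.675 × 0.325) + 0.842 √(0.25 + 0.1275)]² / 0.35². This gives 21.1, so 22 per group, with a one-sided 5% level, and 26.9, so 27, with a two-sided level. The stated 22 therefore reproduces one-sided; 22 / 0.9 = 24.4, so 25 after attrition. None of this concerns harms.

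**Miss rate of the odds-ratio test.** Let a and c be the NMES and control events, two independent binomials with n = 25 each and true risks p1 and p0. Then

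miss = 1 − Σ Bin(a; 25, p1) × Bin(c; 25, p0), summed over tables whose lower 95% limit exceeds 1.

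For the Wald interval the lower limit is exp{ln[a(25 − c) / (c(25 − a))] − 1.96 √(1/a + 1/(25 − a) + 1/c + 1/(25 − c))}.

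| True risk, control → NMES | Wald, zero cells not significant | Wald, 0.5 added to all cells | Fisher exact |
|---|---|---|---|
| 5% → 10% | 99.6% | 99% | 99% |
| 5% → 15% | 97% | 95% | 93% |
| 5% → 20% | 89% | 85% | 80% |
| 5% → 30% | 63% | 48% | 45% |
| 2% → 8% | >99% | >99% | >99% |
| 5% → 20%, 22 per arm | 94% | 90% | 80% |

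Adding 0.5 only to tables with a zero cell gives 83% at 5% → 20%. Unadjusted repeated looks (5 to 25 looks, 40,000 simulated trials) lower the 5% → 20% miss only to 72–76% (Fisher) or 82–83% (Wald with 0.5). For scale, 80% power two-sided needs 76 per arm for 5% v 20% and 206 per arm for 2% v 8%.

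**What the test needs to see.** With 1 of 25 control re-ruptures:

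- 6 of 25 on NMES: odds ratio (6 × 24) / (19 × 1) = 7.58, standard error √(1/6 + 1/19 + 1 + 1/24) = 1.123, lower limit 0.84; Fisher p = 0.098. Not significant.
- 7 of 25 on NMES: odds ratio (7 × 24) / (18 × 1) = 9.33, standard error 1.114, lower limit 1.05; Fisher p = 0.049. Significant.

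**The observed-rate rule, read on the NMES arm.** Above 5% of 25 means above 1.25, so 2 or more events. P(2 or more) = 1 − (1 − p)^25 − 25p(1 − p)^24.

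- p = 5% (no excess): 1 − 0.277 − 0.365 = 36%.
- p = 10%, 15%, 20%: 73%, 91%, 97%.

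Read instead on both arms pooled (3 or more of 50), it trips 46% of the time with 5% in each arm and 96% at 5% v 20%.

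**What the data could exclude.** The exact one-sided 95% upper limit after 0 of 25 is 1 − 0.05^(1/25) = 11%. After 1 and 2 of 25 it is 18% and 23%. With one event in each arm, each Wilson interval is 0.7% to 19.5%, so the Newcombe upper limit for the difference is √[(0.195 − 0.04)² + (0.04 − 0.007)²] = 0.159, or +16 points.

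**The case against.** The strongest reply is that the odds ratio is not the only safeguard. Sections 9.1 and 18.8 compare observed rates with standard of care, name re-rupture, and need no significance. At a true 20% that rule would be reached about 97% of the time, and 6 of 25 would have passed it long before the end. This stands. A reader might infer from the miss rates that the plan as a whole would usually overlook a fourfold rise; the documents do not support that. The 80–89% belongs to the odds-ratio test alone.

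The reply does not rescue the promise in section 10.0. The 18.8 rule names no arm or denominator, does not use the concurrent controls, omits gapping and non-healing, and trips 36% of the time with no excess. It is a trigger and gives no estimate. Section 3.3.1 addresses gapping only as a reason to withdraw an individual participant.

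A second inference to avoid is that the plan equates a non-significant result with safety. It nowhere says so. It says what a lower limit above 1.0 means and leaves the rest unsaid.

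It is also fair that 8.3 presents its AE rule as interim, that 9.7 and 9.8 are monitoring text, that a 95% interval already contains an upper limit, and that 9.7 speaks of AEs or SAEs rather than re-rupture alone. But no other final comparison of harms is described, and pooling re-rupture with events listed at 48% (DVT) and 33% (skin irritation) would say still less about it. Finally, upper bounds will be wide at this size and no margin is proposed here, so the gain is honest reporting rather than a new decision.

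**Conclusion.** The point holds for the between-arm test. Sections 8.3, 9.7 and 9.8 offer one comparison with concurrent controls. At 25 per arm it misses 5% → 20% about 80–89% of the time, depending on the interval method, and 2% → 8% over 99% of the time. It therefore cannot determine whether re-rupture risk is higher, and gapping and non-healing are left to the same test. The plan attaches no meaning to the upper limit, which is the informative end of the interval in a study this small.

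These figures assume re-rupture is analysed on its own, a background within the plan's 2–5%, and a fourfold rise, which the documents do not state. Sections 9.8 and 18.8 also set different interruption criteria, one insensitive and one easily tripped. This is a change that should be made; it does not invalidate the trial.

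**What to change.** In 8.3 and 9.7, specify a final safety analysis by event type: re-rupture, infection, DVT, and gapping or non-healing. For each, report (a) the NMES-arm risk with its exact one-sided 95% upper limit and (b) the NMES-minus-control risk difference with a 95% Newcombe or score interval. Add: *A lower limit at or below 1.0 will not be read as absence of increased risk; the largest excess compatible with the data will be reported.*

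In section 10.0, replace the undertaking to determine whether risk is higher with: *to estimate the difference in risk of these adverse events, with its confidence interval*.

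Sections 9.8 and 18.8 must be reconciled, with the governing rule, arm and denominator stated. No particular stopping rule is proposed here.

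The cost is wording and a few intervals from the trial's own safety data, with no extra patients or visits. The downside is a less favourable statement: after 1 of 25, for example, a re-rupture risk of up to 18% not excluded.

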3.3 Early Withdrawal of Subjects

3.3.1 Criteria for removal from study

Insert subject withdrawal criteria (e.g., safety reasons, failure of subject to adhere to protocol requirements, subject consent withdrawal, disease progression, etc.).

Subject participation will be discontinued by recommendation of the team physician ([name]) if the subject experiences excessive pain during stimulation (>5/10), excessive tendon elongation (>3 cm), gapping at the repair site (>5 mm) or other AEs. Participants will also be removed if the outcomes from the repair surgery require patients to deviate from the standard rehabilitation protocol. An additional criteria include failure of the subject to adhere to the protocol and subject consent withdrawal.

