18.2 Recording of Adverse Events

Address the frequency and process for eliciting adverse event information from research subject, e.g., "Research subjects will be routinely questioned about adverse events at study visits."

In the response, incorporate the following as written:

All adverse events (serious or non-serious) and abnormal test findings observed or reported to study team believed to be associated with the study drug(s) or device(s) will be followed until the event (or its sequelae) or the abnormal test finding resolves or stabilizes at a level acceptable to the investigator.

An abnormal test finding will be classified as an adverse event if one or more of the following criteria are met:

- The test finding is accompanied by clinical symptoms
- The test finding necessitates additional diagnostic evaluation(s) or medical/surgical intervention; including significant additional concomitant drug treatment or other therapy

NOTE: Simply repeating a test finding, in the absence of any of the other listed criteria, does not constitute an adverse event.

- The test finding leads to a change in study drug dosing or discontinuation of subject participation in the clinical research study
- The test finding is considered an adverse event by the investigator.

Research subjects will be routinely evaluated by research team (part of the study team) during visits of the standard rehabilitation protocol.

All adverse events (serious or non-serious) and abnormal test findings observed or reported to study team believed to be associated with the study device(s) will be followed until the event (or its sequelae) or the abnormal test finding resolves or stabilizes at a level acceptable to the investigator.

An abnormal test finding will be classified as an adverse event if one or more of the following criteria are met:

- The test finding is accompanied by clinical symptoms
- The test finding necessitates additional diagnostic evaluation(s) or medical/surgical intervention
- The test finding is considered an adverse event by the investigator.

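### Section 10 promises a between-arm analysis of tendon gapping and non-healing, but no section defines how either is ascertained or sets out an event-specific comparison

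*Combined protocol and SAP*

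**What the plan says.** Section 10.0, after giving a re-rupture rate of 2% to 5% in standard therapy, adds: "Gapping or non-healing of the tendon have also been observed in regular therapy". It then commits the trial to a comparison: "Statistical analysis will be performed to determine if the risk of these adverse events is higher in the intervention group compared to standard therapy".

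Section 3.3.1 lets the team physician remove a participant for "excessive tendon elongation (>3 cm), gapping at the repair site (>5 mm) or other AEs". Section 3.3.2 has participants with these events followed until the event resolves or stabilises.

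The operative safety sections use other lists:

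- 9.1 monitors events "adverse related to Achilles tendon healing (re-rupture, deep vein thrombosis, deep and superficial infection) or the use of NMES (skin irritation and excessive pain"). It also has the team record every adverse event at each visit.
- 9.2 gives three items under tendon healing: re-rupture, deep vein thrombosis and "deep and superficial infection".
- 18.8 interrupts the study if "AEs (re-rupture, deep venous thrombosis, infections, and skin irritation) occur at a rate higher than that reported for standard of care".
- 8.3, 9.7 and 9.8 apply an odds ratio with a 95% interval to adverse events in general. 9.8 suspends the study if the ratio for related and/or serious events becomes significant.

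The ultrasound protocol in 7.2 lists muscle area, fat and skin thickness, tendon length, cross-sectional area at the injury and shear-wave elasticity. Scans are scheduled at weeks 6 and 12. NMES stops at the week-6 visit.

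**The concern.** NMES is meant to load a healing repair, so whether it opens or delays that repair is a natural safety question, and section 10 undertakes to answer it. To do so the trial needs a definition of each event, a way of finding it that is the same in both arms, and a count by arm. None of the three is written down for gapping or non-healing. The removal criterion in 3.3.1 is stated in millimetres, but no study procedure produces that measurement.

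Two things are at stake. A gap without symptoms may never be found. A gap that is found may remove the participant and then survive only as one entry in a pooled adverse-event total, so that the analysis promised in section 10 cannot be reported.

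**Working it through.** **1. Sections side by side**

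| Section | Gapping | Non-healing |
|---|---|---|
| 10.0, promised comparison | named | named |
| 3.3.1, removal | named, above 5 mm | not named |
| 7.2, ultrasound | not listed | not listed |
| 9.1 and 9.2, reviewed data | not named | not named |
| 18.8, interruption | not named | not named |
| 9.1 (all events), 8.3, 9.7, 9.8 | pooled, if noticed | pooled, if noticed |

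**2. Arm size.** Section 8.2 has 22 per group with 10% attrition: 22/0.90 = 24.4, rounded up to 25. This reproduces. The plan gives no rate for gapping or non-healing, so every such rate below is an assumption.

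**3. Can the pooled comparison stand in?** Count a participant as positive if any event occurs. Take the rates in 9.1, assume independent events, and let both arms share the background.

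- Share free of both common events: (1 − 0.48) × (1 − 0.33) = 0.52 × 0.67 = 0.348.
- A difference d in gapping risk therefore appears as 0.348 × d. For an assumed 5% v 20%: 0.348 × 15 = 5.2 percentage points.
- Section 10 attributes skin irritation to the adhesive pads, which controls do not use. If it occurs only with NMES and gapping is 5% in both arms, the any-event risks are 1 − 0.52 × 0.95 = 0.506 and 1 − 0.52 × 0.67 × 0.95 = 0.669. The pooled excess is 16 points with no difference in gapping at all.

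So the pooled figure can hide a tendon effect or show one that is not there. No scan for thrombosis is listed in 7.2, so the observed rate may fall below 48%, and the dilution would then be smaller.

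**4. The same point in counts (assumed).** Controls with any event: 0.48 × 25 = 12. NMES: 12 plus three participants whose only event is a gap, making 15.

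- OR = (15 × 13)/(10 × 12) = 1.63.
- SE of log OR = √(1/15 + 1/10 + 1/12 + 1/13) = 0.572.
- 95% CI = exp(0.486 ± 1.96 × 0.572) = 0.53 to 4.98.

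In a separate row, 3 v 0 gaps would be visible.

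**5. Would an event-specific significance test work?** Apply the plan's rule, lower 95% limit above 1, at 25 per arm.

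- 5 v 1: OR = (5 × 24)/(20 × 1) = 6.0; SE = √(1/5 + 1/20 + 1 + 1/24) = 1.137; lower limit = exp(1.792 − 2.228) = 0.65. Not flagged.
- 7 v 1: OR = (7 × 24)/(18 × 1) = 9.33; SE = √(1/7 + 1/18 + 1 + 1/24) = 1.114; lower limit = exp(2.234 − 2.183) = 1.05. Flagged; six events are not enough.
- Against 0 control events the interval does not exist without a correction. With 0.5 added to each cell, 7 NMES events are needed.

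Exact binomial enumeration of this rule, and the usual two-sided sample size:

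| Assumed control v NMES | Chance of a flag, 25 per arm | n per arm for 80% power |
|---|---|---|
| 2% v 6% | under 0.1% | 376 |
| 5% v 15% | 5% | 141 |
| 5% v 20% | 17% | 76 |
| 10% v 30% | 37% | 62 |

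Naming and measuring the events closes the recording gap. A significance test on them would rarely detect harm.

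**The case against.** The strongest reply is that gapping is already covered. Section 3.3.1 groups it with other adverse events, 3.3.2 follows such events to resolution, and 9.1 records all events at every visit with physician assessment. The odds ratios in 8.3 and 9.7 are not limited to named events, 9.8 can suspend the study on related or serious ones, and 18.6 sends aggregate reports to the safety officer. All of this stands. It answers what happens to a gap once noticed. It does not say how one is noticed, and it does not supply the comparison in section 10.

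Several stronger readings are tempting but unsupported:

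- **Harm to the repair would go unseen.** A reader might infer this from the missing names. Re-rupture is on every list, healing progress is evaluated at weeks 2, 4, 6 and 12, and a recognised gap reaches the pooled analysis. The exposure is limited to gaps without symptoms and to non-healing that nobody defines.
- **Elongation is neglected in the same way.** Section 10 makes no promise about it, and tendon length is a secondary endpoint scanned in both arms at weeks 6 and 12.
- **A silent gap that removes a participant is not an adverse event.** The template text in 18.2 includes "The test finding leads to a change in study drug dosing or discontinuation of subject participation in the clinical research study", and the study's own list leaves that criterion out. But 3.3.1 and 3.3.2 already treat such a gap as an adverse event, so the omission is something to reconcile and not a loss of the event.
- **Gapping must join the interruption list.** 18.8 compares with reported standard-of-care rates, and the documents give none for gapping or non-healing. Whether it belongs there is a clinical decision.

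**Conclusion.** The concern holds in a limited form. As written, the plan cannot deliver the event-specific comparison of gapping and non-healing that section 10 promises, because neither event has a stated method of ascertainment or a separate count by arm. A gap without symptoms can be missed, and the removal criterion in 3.3.1 has no scheduled measurement behind it.

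That the sections disagree rests on the text alone. The size of the consequence cannot be taken from the documents. The 5-point and 16-point figures depend on the rates in 9.1, on independence and on assumed gapping rates. The low chances of a flag hold across the assumed range, up to 37% at 10% v 30%. They argue for counting and describing these events, not for relying on a test.

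**What to change.** 1. In 7.2, add a measurement of the gap at the repair site, in both arms, on the week-6 and week-12 scans already scheduled.
2. State how and when non-healing is ascertained, identically in both arms.
3. Add gapping and non-healing to the data reviewed in 9.1 and 9.2.
4. Report the number of participants with each event by arm, including those removed under 3.3.1, with an exact or score-type interval for the difference. Do not make the conclusion depend on significance.
5. Reconcile 3.3.1, 7.2, 9.1–9.2, 9.7–9.8, 10, 18.2 and 18.8. Whether and how gapping enters the removal or interruption rules, and any threshold, is for the clinical team.

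The cost is one extra measurement on existing scans, some protocol wording and a few table rows. The limit should be stated openly: the first scheduled scan falls at week 6, when NMES stops, so this change gives no early warning during stimulation.
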